### **LevoCept Characteristics**

Study device ease of placement and placement success will be summarized. Cumulative study device expulsion rates will be summarized

### **Adverse Events**

The number and percentage of subjects with each adverse event and serious adverse event will be presented in a table by MedDRA system-organ class and preferred term. Summaries will also be presented by relationship to the LevoCept placement or removal procedure and the severity of the adverse event. All adverse events will be summarized with special attention to those events that may be related to an intrauterine contraceptive, including:

- Acne
- Amenorrhea
- Back pain
- Breast cancer
- Breast tenderness
- Depression/depressive mood
- Dysmenorrhea
- Dyspareunia
- Ectopic pregnancy
- Embedment
- Expulsion, partial or complete
- Headache, migraine
- Intrauterine pregnancy
- Irregular menstrual bleeding
- Leukorrhea
- Ovarian cysts
- Pain and cramping
- Pelvic infection
- Perforation
- Sepsis
- Vaginitis
- Vasovagal reaction immediately after placement

### **LevoCept Safety-Related Removal Rates and Expulsion Rates**

Cumulative LevoCept safety-related removal rates and expulsion rates at each year will be summarized.

#### **Bleeding and Spotting Patterns**

Vaginal bleeding and spotting will be recorded daily by the subject in her e-diary. The ITT and ECYC populations will be used for the bleeding and spotting summaries. The number of bleeding or spotting days will be summarized for each cycle. In addition, bleeding and spotting will be summarized separately. Subjects who discontinue the study due to bleeding complaints prior to completing one 28-day cycle will be included in the bleeding analysis.

#### **Occurrence and Severity of Dyspareunia**

Pain with intercourse will be recorded daily by the subject in her e-diary. The occurrence and severity of dyspareunia will be summarized for each cycle in ECYC population.

#### **Other Safety Assessments**

Changes in vital signs from baseline to each visit will be summarized for the physical examination and vital sign results.

### **20.8 Monitoring of Safety and Pregnancy**

Periodic reviews of safety and pregnancy rates will be conducted by a Medical Monitor. New findings of safety concerns or pregnancies will be communicated to all study sites. A Clinical Events Committee (CEC) will be assembled to review study data if >1 pregnancy is reported.

## **APPENDIX 1. INVESTIGATOR RESPONSIBILITIES**

The Investigator is responsible for ensuring that the clinical study is conducted according to the Investigator Agreement, Clinical Investigational Plan (CIP), all conditions of national regulatory requirements, the governing IRB, and in accordance with the highest standards of medical and ICH E6 Good Clinical Practice (GCP), and the Declaration of Helsinki.

The Investigator(s) shall be responsible for the day-to-day conduct of the investigation as well as for the safety and well-being of the human subjects involved in the clinical investigation. The Investigator(s) shall:

- a) Have the resources to conduct the investigation properly
- b) Ensure that conducting the investigation will not give rise to a conflict of interest
- c) Obtain from the Sponsor the information which the Investigator(s) judges essential about the study device and be familiar with this information
- d) Be well acquainted with the protocol before signing it
- e) Support the monitor and/or auditor, if applicable, in their activities to verify compliance with the protocol, to perform source data verification and to correct the eCRFs where inconsistencies or missing values are identified
- f) Discuss with the Sponsor management any question or modification of the protocol
- g) Make sure that the protocol is followed by all responsible for the conduct of the study at his/her institution. Any deviation shall be documented and reported to the study Sponsor.
- h) Make the necessary arrangements to ensure the proper conduct and completion of the investigation
- i) Make the necessary arrangements for emergency treatment, as needed, to protect the health and welfare of the subject
- j) Ensure that appropriate IRB approvals are obtained prior to the start of the investigation
- k) Provide the communication from the IRB to the study sponsor
- l) Inform the IRB about any serious adverse device effects in accordance with the IRB requirements.
- m) Inform the Sponsor about any adverse events and adverse device effects in a timely manner and in accordance with the timelines laid out in this protocol
- n) Endeavor to ensure an adequate recruitment of subjects
- o) Ensure that the subject has adequate time and information to give informed consent
- p) Ensure that informed consent authorization to release protected health information is obtained and documented prior to any study specific evaluations or procedures being performed

- q) Ensure that clinical records are clearly marked to indicate that the subject is enrolled in this study
- r) Provide subjects with well-defined procedures for any emergency situation and safeguard the subject's interest
- s) Ensure that information which becomes available as a result of the clinical investigation which may be of importance to the health of a subject and the continuation of the investigation shall be made known to: 1) the Sponsor; 2) the subject; and 3) the subject's personal clinician (with the subject's approval), if pertinent to the safety or well-being of the subject
- t) Inform the subject and/or the subject's physician (with the subject's approval) about any premature termination or suspension of the investigation with a rationale for study termination
- u) Have primary responsibility for the accuracy, legibility and security of all investigational data, documents and subject records both during and after the investigation
- v) Review and sign each subject's eCRFs (last page only)
- w) Be responsible for the supervision and assignment of duties at his/her study center
- x) Ensure that all investigational devices are accounted for (number of devices used, discarded and returned to the Sponsor)
- y) Disclose to the Sponsor sufficient accurate financial information to allow the Investigator to submit complete and accurate certification or disclosure statements, and update the information during the course of the investigation and for one year following the completion of the study
- z) Ensure that the Investigator discloses to the Sponsor if the Investigator has ever been associated with terminated research and the reason for such termination is provided
- aa) Ensure that the Investigator discloses to the Sponsor if the Investigator has ever been barred from conducting or participating in clinical research.

End of document -

12.1	Index of Tables.....	24
12.2	Index of Figures	27
12.3	Index of Listings	28
13	Appendix 3 Table Layouts	31
14	Appendix 4 Listing Layouts.....	78

List of Abbreviations

ADaM	Analysis Data Model
AE	Adverse Event
ATC	Anatomical Therapeutic Classification
CDISC	Clinical Data Interchange Standards Consortium
CI	Confidence Interval
ECYC	Evaluable for Cycle Control
EP	Evaluable for pregnancy
ICH	International Conference on Harmonisation
safety	Intent to Treat
LTFU	Long Term Follow up
Max	Maximum
MedDRA	Medical Dictionary for Regulatory Activities
Min	Minimum
n	Number of Patients with an Observation
N	Number of Patients in the Dataset
PD	Protocol Deviation
PT	Preferred Term
SAE	Serious AE
SD	Standard Deviation
SDTM	Standard Data Tabulation Model
SOC	System Organ Class
TLFs	Tables, Listings, and Figures
TEAE	Treatment-emergent AE
WHO DDE	World Health Organization Drug Dictionary Enhanced

1 Introduction

This document details the criteria to be used for the definition of the analysis populations, the statistical methodology for final analysis, and the proposed tabular, graphical and listing presentation of data from Study CMDOC-0022 of Sebela Pharmaceuticals Development LLC (Sebela). This document has been written based on information contained in the final study protocol (version 4.0) dated 18 October 2017.

1.1 Responsibilities

The Biostatistics Department at Synteract Inc. will be responsible for the formal statistical analyses and for the production of the summary tables, data listings, and figures.

1.2 Definitions

The following visits are scheduled in the study protocol:

- Visit 1(Screening Visit);
- Visit 2 (LevoCept Placement Visit): Day1;
- Follow up Visit 3 - 6 : Week 6 \pm 1w,13 \pm 2w, 26 \pm 2w and 52 \pm 2w;
- Long term follow up (LTFU): Every 6 months post 52 weeks (max 3 years post insertion) \pm 2w.

Day 1 is defined as the date of study device successful deployed.

Based on the visit window in the study protocol, new analysis visit windows are redefined as follows to cover every data point, including unscheduled visits. Also note that if there are 2 or more non-missing records in the same analysis visit window, only the last one (by the assessment date) will be used for summary table, but data listings will include all records for all enrolled subjects, unless stated otherwise. For clinical data, visits will be referred to by their study day throughout this document.

The visit windows and study days are presented in Table 1:

Table 1 Visit windows and study days

Visit	Visit (Window) in Protocol	Study Day	Visit (Window) in Protocol in study day	Analysis Visit Window in study day
Visit 1(Screening)	Visit 1/Screening		-1 or earlier	-1 or earlier
Visit 2(Placement)	Visit 2 (Day 1)	1	1	1
Visit 3	Visit 3 (Week 6 \pm 1w)	43	36-56	2 – 68
Visit 4	Visit 4 (Week 13 \pm 2w)	92	78-112	69 – 138
Visit 5	Visit 5 (Week 26 \pm 2w)	183	169-203	139 – 274
Visit 6	Visit 6 (Week 52 \pm 2w)	365	351-385	275 – 385
Visit 7 Long Term FU 1	Visit 7 LTFU 1/Year 2 Month 6 (Week 78 \pm 2w)	547	533-567	386 – 638
Visit 8 Long Term FU 2	Visit 8 LTFU 2/Year 2 Month 12 (Week 104 \pm 2w)	729	715-749	639 – 821
Visit 9 Long Term FU 3	Visit 9 LTFU 3/Year 3 Month 6 (Week 130 \pm 2w)	912	897-930	822 – 1003
Visit 10 Long Term FU 4	Visit 10 LTFU 4/Year 3 Month 12 (Week 156 \pm 2w)	1093	1079-1113	1004 +

The analysis cycles and study days are presented in Table 2:

Table 2 Analysis cycles and study days

Year	Analysis Cycle	Study Day	Year	Analysis Cycle	Study Day	Year	Analysis Cycle	Study Day
Year 1	Cycle 1	1-28	Year 2	Cycle 14	365-392	Year 3	Cycle 27	729-756
Year 1	Cycle 2	29-56	Year 2	Cycle 15	393-420	Year 3	Cycle 28	757-784
Year 1	Cycle 3	57-84	Year 2	Cycle 16	421-448	Year 3	Cycle 29	785-812
Year 1	Cycle 4	85-112	Year 2	Cycle 17	449-476	Year 3	Cycle 30	813-840
Year 1	Cycle 5	113-140	Year 2	Cycle 18	477-504	Year 3	Cycle 31	841-868
Year 1	Cycle 6	141-168	Year 2	Cycle 19	505-532	Year 3	Cycle 32	869-896
Year 1	Cycle 7	169-196	Year 2	Cycle 20	533-560	Year 3	Cycle 33	897-924
Year 1	Cycle 8	197-224	Year 2	Cycle 21	561-588	Year 3	Cycle 34	925-952
Year 1	Cycle 9	225-252	Year 2	Cycle 22	589-616	Year 3	Cycle 35	953-980
Year 1	Cycle 10	253-280	Year 2	Cycle 23	617-644	Year 3	Cycle 36	981-1008
Year 1	Cycle 11	281-308	Year 2	Cycle 24	645-672	Year 3	Cycle 37	1009-1036
Year 1	Cycle 12	309-336	Year 2	Cycle 25	673-700	Year 3	Cycle 38	1037-1064
Year 1	Cycle 13	337-364	Year 2	Cycle 26	701-728	Year 3	Cycle 39	1065-1092
						Year 3+	Cycle 40	1093-1120

2 Objectives

The scientific objective of this study is to evaluate the effectiveness, study device placement, safety, and tolerability of the LevoCept Intrauterine Contraceptive as birth control in parous and nulliparous women of child-bearing age.

The purpose of the study is to obtain the safety and effectiveness data necessary to support initiation of a longer-term Phase III Pivotal Clinical Study for LevoCept.

3 Study Design

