#### **12.3.1 Exit Visit (Visit 2 – Visit 6/Week 52)**

In addition to the assessments in Section 12.3, the following will be performed for subject's exiting the study between Visit 2 – Visit 6/Week 52:

- Transvaginal ultrasound to document LevoCept position
- General physical exam
- Prior to removal of LevoCept, it should be determined if the subject has had vaginal intercourse (with intravaginal ejaculation) within the last 72 hours. If confirmed, LevoCept removal and the Exit visit should be rescheduled. The subject should be instructed to avoid vaginal intercourse for 72 hours or more before LevoCept removal. If rescheduling is not possible, the subject should be instructed not to have intercourse within 72 hours of LevoCept removal due to risk of pregnancy. The subject's preferred method of contraception will be provided at the Exit visit.
  - If the subject elects a non-hormonal method of contraception, a 14-day supply will be provided by the site.

- If the subject elects to use hormonal contraceptive pills as the preferred method of contraception, a one month supply of hormonal contraceptive pills will be provided to the subject by the site as a contraceptive option for the first two weeks following LevoCept removal.
- The subject will also be provided with condoms to take with her as an extra precaution if the subject fails to acquire the contraception noted above.
- In addition to the above, subjects who desire to have LevoCept removed immediately and have had vaginal intercourse (with intravaginal ejaculation) within 72 hours should also be provided with emergency contraception (e.g. ella®, Plan B One-Step®)
- Subject should be reminded to avoid conception within 7 days after LevoCept removal.
- LevoCept Removal
  - LevoCept removal ease
  - LevoCept removal pain
- Urine pregnancy test will be done 17 days after removal/study exit by the subject at home, with a follow up call by the study coordinator or PI required to document results.

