6.2.9.8 Vital Signs

Vital signs (temperature, heart rate, respiration, blood pressure), weight and BMI will be summarized using descriptive statistics at baseline and at each post-baseline time point. Changes from baseline will also be summarized by visit for heart rate, blood pressure, weight and BMI.

Vital signs, weight and BMI will be included in data listings.

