2. Follow a similar format as Table 16.3.6.3.3 for:

Table 16.3.6.3.4 Occurrence and Severity of Menstrual Pain or Cramping by Cycle (ECYC Population)

CONFIDENTIAL

Sebela Pharmaceuticals Development LLC
CMDOC-0022

Page x of y

Table 14.3.7.1
Vital Signs and Weight by Analysis Visit (Safety Subjects)

Parameter (Unit)	Visit Statistic	All Subjects (N=xx)	
		Result	Change from Baseline
Heart Rate (bpm)	Baseline		
	n	xx	
	Mean	xx.X	
	SD	xx.xx	
	Median	xx.X	
	Min	xx	
	Max	xx	
	xxxxx		
	n	xx	xx
	Mean	xx.X	xx.X
	SD	xx.xx	xx.xx
	Median	xx.X	xx.X
	Min	xx	xx
	Max	xx	xx
Respiration (breaths/min)			
SBP (mmHg)			
DBP (mmHg)			
Temperature (F)			
Weight (kg)			
BMI (kg/m2)			

Note: LTFU1= Month 18, LTFU2= Month 24, LTFU3= Month 30, LTFU4=Month 36.
DBP = Diastolic Blood Pressure; SBP = Systolic Blood Pressure; LTFU=Long Term Follow Up.

CONFIDENTIAL

Reference: Listing xxx.

Program Location: \\xx\xxx\xxx\xxx\xxxxxx\xxxxxxxxxxxxxxxxxxxx\xxxx\xxxxx.sas

date

time

Programmer note: Table will continue with all visits and remaining vital signs.

CONFIDENTIAL

Sebela Pharmaceuticals Development LLC
CMDOC-0022

Page x of y

Table 14.3.7.2
BMI Category by Analysis Visit (Safety Subjects)

Visit Statistic	All Subjects (N=xx) n (%)
Baseline	
n	n
Underweight (<18.5)	n (%)
Normal (18.5-24.9)	n (%)
Overweight (25.0-29.9)	n (%)
Obese (>=30)	n (%)
xxxxx	
n	n
Underweight (<18.5)	n (%)
Normal (18.5-24.9)	n (%)
Overweight (25.0-29.9)	n (%)
Obese (>=30)	n (%)

Note: Percentages are based on the number of subjects specified in the column header, i.e. N, unless small n is specified for each category.

Note: LTFU1= Month 18, LTFU2= Month 24, LTFU3= Month 30, LTFU4=Month 36.

LTFU=Long Term Follow Up.

Reference: Listing xxx.

Program Location: \\xx\xxx\xxx\xxx\xxxxxx\xxxxxxxxxxxxxxxx\xxxx\xxxxx.sas

date

time

Programmer note: Table will continue with all visits.

14 Appendix 4 Listing Layouts

CONFIDENTIAL

Sebela Pharmaceuticals Development LLC
CMDOC-0022

Page x of y

Listing 16.2.1.1 Subject Disposition (All Screened Subjects)

Site ID	Subject ID	Date of Placement/ Date of Second Placement Attempt	Complete 12 months of the study	Date of Week 52 Follow-Up Visit or Early Termination/ Subject Status	Transvaginal Ultrasound performed/ Device in Place	Date of Last Exposure to Device/ # of Days on Device [1] Date of Study Completion or Discontinuation/ Date of Last Contact/ # of Days on Study [2]	Primary Reason for Exiting Study/ Desire for pregnancy[3]

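### The SAP's last-record-in-window rule lets an exit visit up to 13 weeks late displace on-time Week 26 vital signs, and the Visit 6 window labels lone early-exit records as Week 52

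*SAP*

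**What the plan says.** SAP 1.2 states that "new analysis visit windows are redefined as follows to cover every data point, including unscheduled visits". Its Table 1 then gives, for each visit, the target study day, the protocol window in study days and the analysis window. The Visit 5 (Week 26) row reads "183 169-203 139 – 274", the Visit 6 (Week 52) row "365 351-385 275 – 385" and the Visit 7 (LTFU 1) row "547 533-567 386 – 638". For windows with several non-missing records the rule is that "only the last one (by the assessment date) will be used for summary table"; listings keep them all.

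The rule feeds the vital-sign summaries. SAP 6.2.9.8 says: "Changes from baseline will also be summarized by visit for heart rate, blood pressure, weight and BMI". Tables 14.3.7.1 (vital signs and weight) and 14.3.7.2 (BMI category) are both laid out by analysis visit. Protocol 20.7, under Other Safety Assessments, plans a summary of vital-sign change from baseline to each visit.

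Exit visits supply the competing records. Protocol 12.3.1 requires its exit procedures "In addition to the assessments in Section 12.3", and Section 12.3 lists vital signs and weight. At unscheduled visits, Protocol 12.6 asks only for evaluations indicated by the reason for the visit.

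**The concern.** A by-visit table should show how women measured at about that visit. Under the last-record rule, a woman seen on time on day 183 who exits on day 270 has two valid records in the Visit 5 window. Her day-183 values are dropped from the table, and the exit values stand for Week 26.

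A second, separate effect comes from the width of the windows. A woman who exits on day 280 has one record in the Visit 6 window, and it is tabulated as Visit 6 although she never reached Week 52.

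In both cases the table row mixes values taken at different times since placement, and some of them come from women who are leaving the study. What is at stake is the timing, and so the interpretation, of the descriptive changes in heart rate, blood pressure, weight and BMI.

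**Working it through.** **Inputs.** Target days and window limits come from SAP 1.2, Table 1. The targets follow week × 7 + 1: 6 × 7 + 1 = 43, 13 × 7 + 1 = 92, 26 × 7 + 1 = 183, 52 × 7 + 1 = 365. For LTFU 3 the SAP gives 912, where the formula gives 911; the SAP's figure is used here.

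**Reproducing the windows.** Most upper limits are midpoints between successive targets, rounded up where needed:

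- Visit 3: (43 + 92)/2 = 67.5, stated 68
- Visit 4: (92 + 183)/2 = 137.5, stated 138
- Visit 5: (183 + 365)/2 = 274, stated 274
- LTFU 1: (547 + 729)/2 = 638, stated 638
- LTFU 2: (729 + 912)/2 = 820.5, stated 821
- LTFU 3: (912 + 1093)/2 = 1002.5, stated 1003

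Visit 6 is the exception. The midpoint is (365 + 547)/2 = 456, but the stated limit is 385, the end of the SAP's protocol window for that visit.

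**How late a displacing record can be.** Under the last-record rule a record displaces the scheduled one only if it is later. The largest lateness is the upper window limit minus the target.

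| Visit | Target | Analysis window | Latest displacing record |
|---|---|---|---|
| Visit 3 | 43 | 2–68 | 68 − 43 = 25 days |
| Visit 4 | 92 | 69–138 | 138 − 92 = 46 days |
| Visit 5 | 183 | 139–274 | 274 − 183 = 91 days (13.0 weeks) |
| Visit 6 | 365 | 275–385 | 385 − 365 = 20 days (2.9 weeks) |
| LTFU 1 | 547 | 386–638 | 638 − 547 = 91 days |
| LTFU 2 | 729 | 639–821 | 821 − 729 = 92 days |
| LTFU 3 | 912 | 822–1003 | 1003 − 912 = 91 days |
| Visit 10 (LTFU 4) | 1093 | 1004 onward | no limit |

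If the scheduled Visit 5 took place on day 169, the start of the SAP's protocol window, the record that displaces it can be 274 − 169 = 105 days later. The same figure at Visit 6 is 385 − 351 = 34 days.

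**How early a lone record can be.** At Visit 6 this is 365 − 275 = 90 days (12.9 weeks). At LTFU 1 it is 547 − 386 = 161 days (23 weeks). An early record loses to any later record in the same window, so these values appear only when no later record exists, as after an early exit.

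**Effect of a closest-to-target rule.** If the scheduled visit falls inside the SAP's protocol window, the tabulated record is at most 203 − 183 = 20 days off at Visit 5 and 385 − 365 = 20 days off at Visit 6. The SAP's upper limits run 6 days beyond target plus two weeks (365 + 14 = 379, against 385). A closest-record rule does nothing for a lone day-275 record, which needs its own row.

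**The case against.** The strongest reply is that taking the last record in a window is prespecified, deterministic and serves the SAP's stated aim of covering every record. The affected tables are descriptive, and SAP 6.2.9 plans no inferential safety analysis. Listing 16.2.9.3 shows each assessment date with its change from baseline, so a substitution can be seen. Clinically significant abnormal vital signs must in any case be recorded as adverse events under Protocol 15.7. All of this stands, and it makes the point a minor one. It does not make an exit value on day 270 a Week 26 value.

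A reader might infer that records 13 weeks off target also replace the scheduled Week 52 visit. They do not. The wide side of the Visit 6 window is the early side, so displacement there is limited to 20 days. The early-exit mislabelling comes from the window width, not from the last-record rule. The note under the protocol's assessment schedule that Visit 6 activities are completed at an early exit explains why those measurements exist; it does not say that they should count as Week 52 values.

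A reader might also infer that displacement favours values from symptomatic women, because extra visits are made for safety issues. The documents do not support this. Vital signs are not mandatory at unscheduled visits, and the rule acts only on non-missing records. Nothing in the documents shows that device complaints shift heart rate, blood pressure, weight or BMI. Exit visits, where vital signs are required, are the firm route.

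The visit labels in the table shells are placeholders. Reading Visit 5 as Week 26 and Visit 6 as Week 52 relies on SAP Table 1, which equates them.

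**Conclusion.** The point holds as a minor defect in a stated rule. At Visit 5 a later record, mainly from an exit visit, displaces the on-time Week 26 vital signs, weight and BMI at up to 91 days after target; the limits for the other visits are in the table above. Separately, a lone early-exit record up to 90 days early is tabulated as Visit 6.

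These are maximum deviations, not expected ones. The documents do not give the number of women with two records in one window, nor the number with a lone early-exit record, so the effect on any mean or change cannot be sized.

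The effect is confined to Tables 14.3.7.1 and 14.3.7.2. The Pearl Index uses placement, removal or expulsion and conception dates with 28-day cycles (SAP 4.1), not these windows, and is unaffected.

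**What to change.** In SAP 1.2, replace the last-record rule along these lines: where an analysis window holds more than one non-missing record, the summary table uses the record of the scheduled visit if there is one, and otherwise the record closest to the target study day, taking the later one on ties. Listings continue to show all records.

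In Tables 14.3.7.1 and 14.3.7.2, show early-exit values in a separate Exit/Early Termination row instead of in the scheduled-visit rows. The shell of Table 14.1.3 already carries an early-termination row, so this follows the SAP's own practice. A removal carried out at an attended scheduled visit would stay in that visit's row.

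The cost is a short SAP edit, one changed selection line in the programs and one extra row per table. The scheduled-visit rows will hold slightly fewer values, because early-exit records no longer fill them.
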